## 5. GENERAL METHODOLOGY AND CONVENTIONS

All statistical analyses will be performed using SAS system version 9.4 or higher.

All summary statistics will be reported stratifying by cohort/dose level (planned or received, depending on the study population) and overall. Relative day 1 is defined as the date of visit “Day 0”, the start of the IP infusion.

### 5.1. Hypotheses and Decision Rules

No formal statistical inference is planned. The analyses will be purely descriptive.

### 5.2. General Methods

#### 5.2.1. Windowing

Windows may be developed for specific data points for analysis.

##### 5.2.1.1. Yearly Windowing

The following windowing option may be used when each yearly observation period used for analysis will be 365 days. Any dates beyond 1460 days will also be included with Year 5 for analysis. Post-infusion AIR and ABR yearly windowing begins with 3 weeks after the IP infusion where day is calculated relative to the IP infusion date. Post-infusion AE yearly windowing begins on the IP infusion date.

Window name	Derivation
Year 1	Day 22 $\leq$ Year 1 $\leq$ Day 365
Year 2	Day 365 < Year 2 $\leq$ Day 730
Year 3	Day 730 < Year 3 $\leq$ Day 1095
Year 4	Day 1095 < Year 4 $\leq$ Day 1460
Year 5	Day 1460 < Year 5

Further details of windowing will be described separately for each endpoint in [Section 2.1](#), as applicable.

### **5.2.2. Analyses for Binary Endpoints**

Descriptive statistics of binary data will include the number of non-missing observations, the frequency of the observed endpoint as well as the observed proportion.

### **5.2.3. Analyses for Continuous Endpoints**

Summary descriptive statistics for continuous variables will include the number of observations with non-missing values, mean, standard deviation, median, first quartile, third quartile, minimum, and maximum values.

### **5.2.4. Analyses for Categorical Endpoints**

Summary tables for categorical variables will include the number and percentage of observations for each category. Unless otherwise specified, the number of observations with non-missing values will be the denominator for percentage calculation.

## **5.3. Methods to Manage Missing Data**

In general, missing data will not be imputed in this study, unless specified in [Section 3](#), where individual endpoints are discussed.

### **5.3.1. COVID-19 Considerations**

In order to assess the effect of COVID-19, the following information will be additionally listed or summarized separately for the study:

- AE associated with COVID-19.
- Protocol Deviations related to COVID-19 (important and non-important ones).

Additional COVID-related data presentations or analyses may be provided, as appropriate.

## **6. ANALYSES AND SUMMARIES**

### **6.1. Primary Endpoints**

#### **6.1.1. Incidence of Adverse Events and Serious Adverse Events**

During Years 1, 2, and 3 all AEs are to be collected, and during Years 4 and 5, treatment-related AEs (plus all-causality SAEs) are to be collected.

Incidence of adverse events will be presented descriptively. In addition, incidence of treatment-related adverse events will be similarly presented. Summaries will be presented by dose level and overall. AE tables by year will show columns for each dose level and overall, and separate pages for each of the five yearly periods as described in [Section 5.2](#) (Year 1, 2, 3, 4, and 5), with denominator (number of participants still being followed at the beginning of each year) and counts (%) of participants in each, corresponding to the onset date of AE.

The incidence and severity of AEs will be tabulated and grouped by system organ class (SOC) and preferred term (PT). In addition, all serious AEs (regardless of causality) will be summarized separately. A summary table including severity graded by CTCAE version 4.03, for those events that are possible to rate, will also be provided.

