## 2.2. Study Design

### Number of Participants:

Approximately 20 participants may be enrolled in this study. The dose selection and number of participants studied at each dose level will be based on safety and the cumulative kinetics of circulating FVIII levels observed in previously dosed participants.

[figure not shown]

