### Intervention Groups and Duration:

The possible clinical dose level range will be from  $6 \times 10^{11}$  vector genome (vg)/kilogram (kg) to  $6 \times 10^{13}$  vg/kg, with a starting dose of  $9 \times 10^{11}$  vg/kg, which is expected to yield >5% normal FVIII levels in 57% of treated participants. Several dose levels may need to be studied to identify a safe and tolerable therapeutic range. If observed FVIII levels at the starting dose level of  $9 \times 10^{11}$  vg/kg are higher than anticipated, then dose de-escalation to  $6 \times 10^{11}$  vg/kg will be considered.

Dose levels considered include:

Possible Total Recombinant Adeno-Associated Viral Vector (rAAV) Dose (vg/kg)
$6 \times 10^{11}$
$9 \times 10^{11}$
$1.2 \times 10^{12}$
$2 \times 10^{12}$
$4 \times 10^{12}$
$6 \times 10^{12}$
$1 \times 10^{13}$
$2 \times 10^{13}$
$3 \times 10^{13}$
$4 \times 10^{13}$
$5 \times 10^{13}$
$6 \times 10^{13}$

The duration of study participation will be approximately 62 months for each participant, divided into approximately 8 weeks (2 months) for screening, and 60 months study follow-up following a single infusion on the visit, "Day 0". Accrual is planned for 20 months.

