### 6.6.1. Adverse Events

All AEs will be summarized for the Safety population, by dose level and overall across dose groups. AEs by Year 1, 2, 3, 4, and 5 will be presented.

Both all-causality AEs and treatment-related AEs will have similar summaries presented descriptively. All data will be included in the summary as appropriate, with clarifying footnotes describing the types of AEs collected in each reporting period.

The number and percentage of participants with any TEAE, any treatment-emergent SAE, any treatment-related TEAE, any serious treatment-related TEAE, and any TEAE leading to discontinuation from the study will be presented for all participants by dose level and overall.

All TEAEs, treatment-emergent SAEs, and treatment-related TEAEs will be summarized by SOC and PT; all TEAEs and treatment-related TEAEs will also be summarized by SOC, PT and Common Terminology Criteria for Adverse Events (CTCAE; version 4.03) severity grade. Summaries will include the number and percentage of participants in each SOC, PT, or CTCAE severity grade by dose level and overall. Adverse events of special interest (AESI) will be identified in summaries by SOC and PT.

Separate listings of TEAEs, SAEs, TEAEs leading to discontinuation from the study, and AEs leading to death (if any) will be produced. A listing of deaths will be provided as well, including the date and information about the primary reason for death.

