### **7. INTERIM ANALYSES**

#### **7.1. Introduction**

An interim analysis (IA) of safety and efficacy data will be conducted at one year after the last enrolled participant receives SB-525 (PF-07055480) infusion. As this is an open-label study, the sponsor may conduct unblinded reviews of the data during the course of the study for the purpose of safety assessment, facilitating dose escalation decisions, facilitating pharmacokinetic/pharmacodynamic modeling, and/or to support clinical development.

Additionally, an interim analysis of safety and efficacy data may be conducted to support interactions with the national or local health authorities related to the submission and/or registration of SB-525 (PF-07055480) for use in hemophilia A patients.

This study will use an external Data Monitoring Committee (eDMC). The eDMC is independent of the study team and includes only external members. The eDMC will convene approximately every 6 months until study completion to monitor the safety and efficacy of the participants. Ad-hoc meetings will be organized as needed [eg, to assess events of special interest or after receipt of a serious unexpected suspected adverse reaction (SUSAR)]. Specification details for the process and the outputs to be generated for eDMC review will be provided in the eDMC charter.

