## **7.2. Interim Analyses and Summaries**

The IA summaries will be a subset of the analyses described in this SAP, with the calculations of the observation period for a participant being based on the date of discontinuation or the date of the interim analysis data cut (ie, observation period = date of data cut [or conclusion date] – date of IP infusion + 1). Possible outputs include ABR, AIR, FVIII activity, safety, and other exploratory endpoints.

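### By-year AE percentages use a start-of-year head count, so if produced at a staggered cut such as the planned interim, Years 2 and 3 would understate full-year incidence

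*SAP*

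**What the plan says.** SAP 6.1.1 plans AE tables with a page per year and columns for each dose level and overall. A participant is counted in the year of AE onset, and the denominator is the "number of participants still being followed at the beginning of each year". SAP 6.6.1 repeats the commitment: "AEs by Year 1, 2, 3, 4, and 5 will be presented". SAP 5.2.1.1 sets the windows: "each yearly observation period used for analysis will be 365 days", and "Post-infusion AE yearly windowing begins on the IP infusion date".

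The interim analysis is to be "conducted at one year after the last enrolled participant receives SB-525 (PF-07055480) infusion" (SAP 7.1). SAP 7.2 gives its content: "The IA summaries will be a subset of the analyses described in this SAP", with safety named among the possible outputs. SAP 7.1 also allows further interim analyses to support dealings with health authorities. On timing and size, SAP 2.2 says "Accrual is planned for 20 months" and "Approximately 20 participants may be enrolled in this study".

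Three other places bear on the point:

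- Post-infusion infusion and bleeding rates are divided by each participant's observed days (SAP 3.2.1 and 3.2.2), so the plan does use time at risk elsewhere.
- SAP 6.5.2 plans a participant-level listing of the years entered and the time spent in each, as of the data cut.
- The AE table footnotes in SAP 6.6.1 are to explain which kinds of AE were collected in each period. They do not cover incomplete follow-up.

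**The concern.** A participant who entered Year 2 a week before the cut counts as one whole person in the Year 2 denominator but has had one week in which to contribute an event. At a cut with staggered entry this applies to much of the Year 2 denominator and, on the planned timeline, to all of the Year 3 denominator. An unchanged AE risk would then look like a falling one. All AEs are collected through Year 3, so narrower collection cannot explain a drop between Years 1 and 3.

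Dose columns within a year are affected as well. Cohorts are dosed in sequence, so the last cohort has the shortest follow-up in Year 2. That is cohort 4 if dosing follows the numbering in SAP 6.5.3, and SAP 3.1.2.1 identifies its dose as the one intended for Phase 3. Safety is the first primary objective and the analyses are descriptive only (SAP 5.1), so the displayed percentages are what a reader will interpret.

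**Working it through.** The documents give no by-year AE percentage or exposure figure, so there is no stated number to reproduce. The check is follow-up arithmetic.

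**Inputs from the documents.** Accrual 20 months (SAP 2.2); cut 12 months after the last infusion (SAP 7.1); windows of 365 days, taken as 12 months, from infusion (SAP 5.2.1.1).

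**Assumptions not in the documents.** Uniform entry over accrual, no dropout and, for the percentages only, a constant hazard.

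**Observed time.** The cut is at month 20 + 12 = 32, so follow-up F is uniform on 12 to 32 months.

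- Year 1: everyone has 12 of 12 months.
- Year 2: observed time is min(12, F − 12), where F − 12 is uniform on 0 to 20. The share with a complete year is 8/20 = 40%. The mean is (12/20) × 6 + (8/20) × 12 = 3.6 + 4.8 = 8.4 months (70%).
- Year 3: entered if F > 24, which is 8/20 = 40%, or about 8 of 20 participants. Observed time is uniform on 0 to 8, mean 4 months (33%). Nobody has a complete year.

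**Displayed percentage.** For a true full-year incidence p, let Λ = −ln(1 − p) be the yearly hazard.

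- Year 2 shows 0.4 × p + 0.6 × (1 − p/Λ).
- Year 3 shows 1 − (1 − e^(−2Λ/3)) / (2Λ/3), since the maximum is 8 of 12 months.

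For p = 50%, Λ = 0.693:

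- Year 2: 0.4 × 0.5 + 0.6 × 0.279 = 36.7%.
- Year 3: 1 − 0.370/0.462 = 19.9%.

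For p = 30%, Λ = 0.357:

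- Year 2: 0.4 × 0.3 + 0.6 × 0.159 = 21.5%.
- Year 3: 1 − 0.212/0.238 = 11.0%.

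**Sensitivity at a true 50%.**

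| Entry pattern | Year 1 | Year 2 | Year 3 | Year 4 |
|---|---|---|---|---|
| Uniform, 20 months | 50% | 36.7% | 19.9% | – |
| Staggered about 6 weeks apart early on, 20 months | 50% | 34.8% | 20.9% | – |
| Uniform, 12 months | 50% | 27.9% | none entered | – |
| Uniform, 30 months | 50% | 41.1% | 35.2% | 15.5% |

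The size changes but the direction does not.

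**Dose columns.** Two successive 6-week follow-ups in each of cohorts 1 to 3 (SAP 2; four cohorts in SAP 6.5.3) put the start of cohort 4 at 3 × 2 × 6 = 36 weeks or later, about 8.3 months. At a month-32 cut its first participant has at most 32 − 8.3 = 23.7 months, so cohort 4 has nobody in Year 3. In the staggered run, with 6 participants in cohorts 1 to 3 and 14 in cohort 4 (an assumed split), mean Year 2 follow-up is 12 months in the earlier cohorts and 5.9 months in cohort 4. A true 50% would show as 50% and 27.8%.

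**Effect of using time at risk.** With time stopped at the first event, events divided by participant-years returns Λ in every window under a constant hazard. For p = 50% that is 0.69 per participant-year in each of Years 1, 2 and 3.

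**The case against.** Several counter-arguments have force.

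- **The interim need not contain these tables.** SAP 7.2 describes a subset and lists possible outputs, and the further interim analyses in SAP 7.1 are optional. A reader might infer that the interim will show a false decline. The documents support only that it could. This stands, and makes the point conditional.
- **Short follow-up is disclosed.** With about 20 participants, the SAP 6.5.2 listing lets a careful reader see the time each person spent in each year. That is a real mitigation, but it does not enter the percentages or the table footnotes.
- **The percentage is openly defined.** It is an observed proportion to date, and it understates only a full-year incidence that the SAP does not claim to estimate. That is fair, but putting it beside a complete Year 1 invites the comparison.
- **A constant hazard is doubtful.** This is a single infusion; Protocol 6.1.1 describes side effects following administration, and Protocol 10.7 concentrates liver monitoring through Week 20. A reader might take the whole fall from 50% to 20% as artefact. The documents do not support that, since some decline may be real. The table could not tell the two apart.
- **Later cohorts and later years.** A reader might infer that cohort 4 would look safer in Year 3. On the planned timeline it has nobody there, so the between-dose distortion is confined to Year 2.
- **By-year tables are supplementary.** SAP 3.5.1 adds them to whole-study AE reporting. This limits the weight of the point but does not answer it.

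**Conclusion.** The point holds in conditional form. Nothing in the SAP adjusts the by-year AE denominator for time observed within the year. If the tables are produced at the planned interim, or any cut with staggered follow-up, percentages for incomplete years understate full-year incidence of any AE that is still occurring.

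On the planned timeline about 60% of the Year 2 denominator and all of the Year 3 denominator would be incomplete. The observed-time figures rest on planned accrual, uniform entry and no dropout. The displayed figures of about 50/37/20% (true 50%) and 30/22/11% (true 30%) also need a constant hazard and are illustrations, not predictions. Year 3 is affected only if accrual exceeds 12 months, as planned.

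A reader might extend the criticism to the final analysis. With 60 months for everyone the windows are complete, and only withdrawals leave part-years in a denominator. This is a modest presentation weakness with a cheap remedy.

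**What to change.** In SAP 6.1.1 and 6.6.1:

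- Add participant-years at risk for each yearly window, by dose level and overall.
- Beside n (%), report exposure-adjusted incidence: participants with the event per participant-year, with time stopped at the first event in the window, withdrawal or data cut.
- At interim cuts, footnote how many participants in each denominator have a complete year, and do not present a percentage alone for an incomplete year.

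The cost is SAP wording, one derived variable and an extra column; no new data are needed, because time in each year is already to be derived for the SAP 6.5.2 listing. Three limits should be understood. Rates will be unstable in the smallest dose columns, as the percentages are. A crude rate treats the hazard as constant within a window. The rate and the percentage also differ numerically even with complete follow-up (50% corresponds to 0.69 first events per participant-year), so the column needs a clear label.

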### **6.1.2. FVIII Activity**

Summary tables for central laboratory FVIII activity values, with descriptive statistics by study visit and dose level will be created. The FVIII activity values assessed by the two assays (chromogenic and one-stage clotting) will be summarized separately. Listings will be presented separately for local and central laboratory individual values, as described in [Section 3.1.2](#).

Individual plots of FVIII activity will be created using the Safety population, with collection time in weeks post-infusion on the x-axis (including unscheduled visits), and FVIII activity on the y-axis. Separate figures will be created for one-stage clotting and chromogenic results; each figure will contain all participants from a cohort on the same graph. The plots will be created using both the original scale and the log scale.

A scatter plot of chromogenic assay versus one-stage assay results will be generated to investigate the correlation between the two assays. Measurements from all time points will be placed on the same graph, and thus a participant will contribute multiple times to the figure. Data points will be differentiated by different colors for cohorts and symbols for participants.

All FVIII analyses will be performed using the Safety analysis set. Additional analyses may be performed using an Evaluable population, if appropriate.

#### **6.1.2.1. FVIII Activity Geometric Mean**

The geometric mean of FVIII activity between the week determined to be the start of steady state (Week 9), and Week 52 (Year 1) will be summarized for Cohort 4 ( $3 \times 10^{13}$  vg/kg) by type of assay (chromogenic and one-stage). The geometric mean of FVIII activity will also be summarized for each additional yearly interval as specified in [Section 3.1.2.1](#).

## **6.2. Secondary Endpoints**

### **6.2.1. Annualized Infusion Rate**

Both pre- (for any reason and reasons other than prophylaxis) and post-IP infusion annualized rates will be summarized together, along with the difference and percent reduction with respect to the pre-IP infusion AIR (for any reason), using the Safety population by dose level. All participants, regardless of prior prophylaxis treatment status, will be included. AIR will be summarized by the time intervals as specified in [Section 3.2.1](#).

Additional analyses may be performed using an Evaluable population, if appropriate.

Listings of FVIII replacement therapy and the annualized rates will be provided.

### 6.2.2. Annualized Bleeding Rate

Both pre-screening and post-IP infusion total ABRs will be summarized together with the difference and percent reduction, along with the summary of post-IP infusion treated ABR, for the Safety population by dose level. The number and percentage of participants with no bleeds post-IP infusion will also be summarized by dose level. All participants, regardless of prior prophylaxis treatment status, will be included. Post-IP infusion treated and total ABR will be summarized by the time intervals as specified in [Section 3.2.2](#).

Separate summaries of treated and total post-IP infusion ABR by location type (joint, target joint, soft tissue/muscle/other), by cause (spontaneous and traumatic BEs), and by BE severity will be created for the Safety population stratifying by dose level.

Additional analyses may be performed using an Evaluable population, if appropriate.

Listings of BEs recorded during the study and the annualized rates will be created. The listing will additionally include treated and total post-initiation or post-resumption of prophylaxis ABR for the participants who initiated or resumed a FVIII prophylaxis treatment during the post-infusion period.

### 6.2.3. EQ-5D-5L

EQ-5D-5L VAS score and Index score results and change from baseline will be summarized as continuous variables by visit, stratifying by dose level (cohort) and overall (across dose levels).

For EQ-5D-5L dimensions, summary will be provided with counts and percentages of scores in each dimension by visit.

Listings of EQ-5D-5L dimension scores, VAS score, and Index score data will be created.

### 6.2.4. FVIII Inhibitor

The number and percentage of participants with negative results at each visit will be presented.

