
 To evaluate clinical impact (efficacy and quality of life) on hemophilia after dosing with SB-525 (PF-07055480). 	
 Change from baseline in use of FVIII replacement therapy and frequency and severity of bleeding episodes Change from baseline in the EQ-5D-5L

 To evaluate immune response to FVIII. 	
 Measurements of FVIII inhibitor levels

 To evaluate vector shedding of AAV2/6. 	
 Detection of AAV2/6 vector DNA by PCR in plasma, saliva, urine, stool and semen
Exploratory objectives	Exploratory endpoints

 To evaluate the concurrence between FVIII levels by ELISA (FVIII antigen) and by FVIII activity assays 	
 Measurements of FVIII antigen levels

 To further investigate SB-525 (PF-07055480) mechanism of action and the immune response 	
 Measurements of neutralizing activity and antibodies to AAV2/6, as well as T-cell responses to AAV2/6 and FVIII Measurements of von Willebrand factor (vWF), C-reactive protein (CRP), and IL6
Optional liver biopsy substudy only: 
 To evaluate vector integration in the liver To evaluate the histopathology of the liver tissue To assess the expression of protein and/or RNA levels of FVIII and other biomarkers of interest in the liver 	
 For the integrations analyses (as feasible, i.e. depending on the quantity of biological material collected): the number and location of integration sites, the location of the integration sites relative to transcription start sites, the nature of the inserted sequence, the frequency of insertions, and the frequency and distribution for each size and type of insertion Other exploratory endpoints (as feasible): histopathology assessment (eg. presence of fibrosis assessment, presence of lymphocytic invasion), protein and/or

Objectives	Endpoints
	RNA expression of FVIII and selected biomarkers (eg. Grp78, Gal3BP)

Overall Design:

SB-525-1603 (C3731001) is a phase 1/2, open-label, single-dose, dose-ranging study. The dose selection and number of participants studied at each dose level will be based on safety and kinetics of circulating FVIII levels observed in previously dosed participants.

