8.2.13.2. FVIII Inhibitor Titer

FVIII inhibitor levels will be measured as displayed in the SoA ([Table 1](#)). Weekly assessments (through Week 52) may be required if a participant is receiving steroids or develops an inhibitor. After Week 52, measurement of FVIII inhibitor titer may increase if warranted by changes in FVIII activity or the presence of inhibitor.

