9.4.2. Secondary Endpoints Analyses

The clinical impact on hemophilia after dosing with SB-525 (PF-07055480) will be determined from the summarization of the change from baseline in the use of FVIII

replacement therapy and the frequency and severity of bleeding episodes. Changes from baseline in the EQ-5D-5L will also be summarized.

The immune response to SB-525 (PF-07055480) will be evaluated from the summarization of FVIII inhibitor levels. Summarization of vector shedding data will include vector DNA detection by PCR in plasma, saliva, urine, stool, and semen.

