		
Corrected the definition of which numerical values are considered nAb positive (3.3.2).
 
Updated summaries related to FVIII steady state. (sections 3.3.5 and 6.3.6).
 
Added clarifying text on which AEs are considered TEAEs (section 3.5.1) and updated AE summaries presented (section 6.6.1).
 
Removed summary/listing of assessments not performed before, during and after the COVID 19 period (section 5.3.1).
 
Removed plot of FVIII activity vs. number of treated bleeding episodes calculated at 4 week and/or 2 week intervals (section 6.1.2).
 
Clarified that the summary of geometric mean of FVIII activity is applicable to Cohort 4 only (section 6.1.2.1).
 
Added the option of performing analyses using an Evaluable population for AIR and ABR (sections 6.2.1 and 6.2.2)
 
Added listing of post-initiation of prophylaxis treated and total ABR for participants who initiated or resumed a FVIII prophylaxis treatment during the post-infusion period (section 6.2.2).
 
Removed shift tables from baseline to each time point of EQ-5D-5L dimensions (section 6.2.3).
 
Removed data listing of FVIII inhibitor titer (section 6.2.4).
 
Added summary of Von Willebrand Factor observed values and change from baseline (section 6.3.4).
 
Removed vital signs from baseline summaries (section 6.5.1).

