### 3.1.2. Factor VIII Activity

All samples collected from participants for plasma factor FVIII activity levels will be analyzed by central and local laboratories. In the central laboratory, FVIII activity will be assessed both by chromogenic and one-stage clotting assays. In local laboratories, FVIII activity will be assessed by chromogenic or one-stage clotting assay based on local laboratory's usual practice. Only central laboratory results will be used for analysis. Raw values reported as below the limit of quantification (BLoQ) will be converted to a numeric value for analyses (summaries and plots). The numeric value of 0.009 international units (IU)/ milliliter (mL), or 0.9 % normal, will be assigned prior to analysis for both one-stage clotting assay and chromogenic assay when the originally reported results were <0.010 IU/mL and <0.030 IU/mL, respectively. Summary tables and plots will use "% normal" as units, where % normal = IU/ mL x 100.

FVIII activity assessments assigned to a protocol-defined visit, will be analyzed for that visit. If FVIII activity is assessed as an unscheduled visit, the assessment date will be converted to a day relative to the investigational product (IP) infusion and divided by 7. The integer value of the quotient will be the 'week' assigned to the unscheduled assessment. If the derived week for an unscheduled assessment falls within the visit window of a protocol-defined visit, the unscheduled assessment result will be included in summaries and analyses for the mapped protocol-defined visit. Additional windowing details for mapping weeks to visits can be found in the Analysis and Reporting plan.

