### 3.2.4. FVIII Inhibitor

FVIII inhibitor assessments will be collected according to protocol-specified SoA. Results provided by the central laboratory as <0.6 Bethesda units (BU) will be considered as negative.

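### SAP 6.2.4 reduces the FVIII inhibitor-level endpoint to percent negative per visit, so the endpoint analysis shows neither titre nor how many participants were ever positive

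*SAP*

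**What the plan says.** **Endpoint.** The synopsis and Table 2 of the protocol set the secondary endpoint for immune response to FVIII as "Measurements of FVIII inhibitor levels". Protocol 9.4.2 says this response "will be evaluated from the summarization of FVIII inhibitor levels".

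**Derivation and analysis.** SAP 3.2.4 gives one rule: "Results provided by the central laboratory as <0.6 Bethesda units (BU) will be considered as negative". SAP 6.2.4 consists of one sentence: "The number and percentage of participants with negative results at each visit will be presented". The current section has no titre summary, peak value, time of first positive, count of participants ever positive, or listing. SAP section 1 records that version 3 took a titre listing out of 6.2.4. That is not an error in itself, but it shows that the absence is intended.

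**Extra sampling.** Protocol 8.2.13.2 adds tests to the schedule: "Weekly assessments (through Week 52) may be required if a participant is receiving steroids or develops an inhibitor", and "After Week 52, measurement of FVIII inhibitor titer may increase if warranted by changes in FVIII activity or the presence of inhibitor". Footnotes l and n of the Schedule of Activities say much the same.

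**Placing extra samples.** The visit-mapping rule in SAP 3.1.2 begins "If FVIII activity is assessed as an unscheduled visit, the assessment date will be converted to a day relative to" the infusion. It is written for FVIII activity. No matching rule is given for inhibitors, and SAP 5.2.1 says only that windows may be developed for particular data.

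**The concern.** A level is a measured quantity, and percent negative is not a summary of it. A result of 0.6 BU and one many times higher produce the same table. A per-visit percentage is also a cross-section. It does not follow participants from row to row, so it does not answer the first question a reader will ask: how many treated participants developed an inhibitor?

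The study is purely descriptive (SAP 5.1) with about 20 participants, so the description is the result. Less central laboratory measures get fuller treatment. Vector shedding has peak values, times and listings (SAP 6.2.5), FVIII antigen is summarised and listed (6.3.1), and AAV2/6 antibodies and ELISPOT results are listed (6.3.2). Inhibitor titre is not among the items listed in 6.3.2.

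The extra samples come from participants on steroids, with an inhibitor or with changing FVIII activity. Those are the samples in which an inhibitor finding would matter most, and 6.2.4 does not say where they go.

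**Working it through.** The plan gives no figure on this point to reproduce. The check is what the planned table can and cannot show.

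**1. Scheduled inhibitor draws after infusion (Schedule of Activities).**
- Day 1: 1
- Weeks 4, 8 and 12: 3
- Weeks 16 to 52, every 4 weeks: 10
- Six-monthly after Week 52, Months 18 to 60: 8
- Total: 1 + 3 + 10 + 8 = 22, plus an early-termination draw where one applies.

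Weekly testing through Week 52 could add up to 52 − 13 = 39 week-points that are not scheduled inhibitor visits.

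**2. Can the table give the number ever positive?** Let p_v be the number positive at visit v, among N participants with complete data. The number ever positive can lie anywhere from max(p_v) to min(N, Σp_v).
- Assumed cohort of 5, one positive at each of two different visits: both rows show 4/5 = 80% negative. The bounds are 1 and 2, so ever-positive is 1/5 = 20% or 2/5 = 40%.
- All 20 participants, one positive at each of the 22 visits: every row shows 19/20 = 95% negative. The bounds are 1 and min(20, 22) = 20, so ever-positive can be anything from 5% to 100%. This is an extreme case to show the range, not a forecast.

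Missing samples widen the ambiguity, because SAP 5.2.4 uses non-missing observations as the denominator, which can change from visit to visit.

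**3. Can the table give titre?** No. Each result enters only as below 0.6 BU or not.

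**4. Could a positive be absent from every row?** Only if it is found at an extra draw that is not mapped to a visit, and is gone by the next scheduled draw. If onset is uniform over a gap of g weeks and the inhibitor lasts d weeks, the chance that it falls wholly between scheduled draws is max(0, 1 − d/g). The documents give no durations, so d is an assumption.

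| Gap g | d = 2 | d = 4 | d = 8 | d = 13 | d = 26 |
|---|---|---|---|---|---|
| 4 weeks (Weeks 4 to 52) | 0.50 | 0 | 0 | 0 | 0 |
| 26 weeks (after Week 52) | 0.92 | 0.85 | 0.69 | 0.50 | 0 |

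For example, 1 − 8/26 = 0.69. These are chances of falling between scheduled draws. They are not chances that an inhibitor occurs, or that an extra draw catches it. If one participant in an assumed cohort of 5 were positive only at such a draw and it was not mapped, all 22 rows would read 100% negative against 1/5 = 20% ever positive.

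**The case against.** **The SAP may summarise inhibitors elsewhere.** A reader might infer that percent negative is the only inhibitor output in the whole SAP. The documents do not support that. SAP 6.6.2 says, without qualification, that the tests in SAP 3.5.2 will be summarised. SAP 3.5.2 points to Protocol Appendix 2, which lists FVIII inhibitor testing. The restriction to selected parameters applies only to the low/normal/high tabulations. The same section plans a shift table of minimum and maximum on-study records. This stands as a limit on the point. Even so, 6.6.2 does not name inhibitor titre or any statistic for it, and 6.2.4 does not refer to it.

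**Adverse event tables count participants.** Protocol 10.3.1 requires some abnormal laboratory results to be recorded as adverse events, including those needing additional diagnostic testing. An inhibitor that prompts weekly testing arguably qualifies. Immune parameters are part of the primary adverse event endpoint (SAP 3.1.1), and SAP 6.6.1 counts participants by preferred term. So it would be wrong to say that capture rests on clinical judgement alone. But 10.3.1 also has an exclusion for findings tied to the underlying disease, Protocol 8.3.1 narrows non-serious event collection from Month 36, and no adverse event table reports titre.

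**Extra samples are not excluded.** A reader might infer that results between scheduled visits drop out of the endpoint. The SAP is silent on them, and 5.2.1 leaves room for windows. Weekly testing prompted by an inhibitor presupposes that one was already detected, so that route alone cannot leave every row negative. What remains is a transient inhibitor first found at a steroid-prompted draw, or at an added draw after Week 52.

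**The SAP may depart from the protocol.** Both documents allow it, and only major changes to primary endpoints need an amendment. So this is not a procedural breach. The objection is to what the table leaves out.

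**Conclusion.** The point holds for the endpoint analysis. As written, SAP 6.2.4 does not summarise levels, shows no titre, and cannot give the number of participants ever positive. These three statements follow from the text and need no assumption about how often inhibitors occur.

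The part about extra samples is narrower and rests on silence. 6.2.4 gives no rule for them, and only an inhibitor that clears before the next scheduled draw could be missing from every row. Between Weeks 4 and 52 it would have to last less than about 4 weeks. After Week 52 the window is about 26 weeks, so the gap matters more there.

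The cohort of 5, the inhibitor durations and the uniform onset are illustrative assumptions. The documents give no inhibitor frequency and do not show that loss is likely. No decision rule in the SAP depends on this table, so this is a change that should be made rather than a flaw that undermines the study.

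**What to change.** Keep the per-visit table and add to SAP 6.2.4, by dose level and overall:

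- the number and percentage of participants with at least one post-infusion central laboratory result of 0.6 BU or more at any time, including unscheduled and early-termination samples;
- the peak titre and the time of first positive result for each such participant;
- a listing of positive titres with dates.

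The 0.6 BU cut is the one SAP 3.2.4 already uses. Counting results at any time means that the ever-positive figure does not depend on how extra samples are mapped. One added sentence should say whether such samples also enter the per-visit rows.

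The cost is SAP wording, one small table and one listing, all from data already collected.
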